### 6.10.3 Sensitivity Analyses

- Repeat the primary efficacy analysis with the Per Protocol Population
- Use an analysis of covariance (ANCOVA) with treatment group, background AD-specific therapy, CDR-Global Score as main effects and the baseline z-score as the covariate to compare Z-scores of total recall and delayed recall on the HVL T-R at Week 24 in the neflamapimod and placebo groups

The results of the ANCOVA will be summarized using the treatment groups' least square means, the difference between the treatment groups' least square means, the 95% confidence interval for the treatment group difference and the p-value.

#### 6.10.4 Secondary Analyses

The secondary efficacy endpoints at Week 24 and follow-up when applicable are:

- Change in WMS immediate and delayed recall composites in neflamapimod-treated subjects compared to placebo-recipients.
- Change in CDR-SB in neflamapimod-treated subjects compared to placebo-recipients.
- Change in MMSE in neflamapimod-treated subjects compared to placebo-recipients.
- Change in CSF biomarkers (T-tau, P-tau181, A $\beta$ 1-40, A $\beta$ 1-42, neurogranin, neurofilament light chain) in neflamapimod-treated subjects compared to placebo-recipients at the end of treatment.

The same method used for the primary efficacy analysis will be applied for the analyses of the change in WMS and change in CDR-SB.

Changes in MMSE and CSF biomarkers will be compared using an analysis of covariance (ANCOVA) with treatment group, background AD-specific therapy, CDR-Global Score as main effects and the baseline assessment as the covariate. The results of the ANCOVA will be summarized using the treatment groups' least square means, the difference between the treatment groups' least square means, the 95% confidence interval for the treatment group difference and the p-value. Scale Plots of Mini-Mental State Examination (MMSE) Score by Visit and by Treatment; and Baseline and Change from Baseline to Day 84 MMSE Score.

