### 4 SAMPLE SIZE

Up to 76 subjects per treatment arm (152 total) provides 90% power to detect ES of 0.53 and 80% power to detect ES of 0.46. This level of ES is the minimum treatment effect amount considered clinically relevant and is less than the effect size seen in the Phase 2a studies.

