### 5 RANDOMIZATION

Randomization was stratified by 1) background AD-specific therapy (cholinesterase inhibitor or memantine versus no cholinesterase inhibitor or memantine); and 2) CDR-Global Score of 0.5 versus 1.0.

Eligible subjects were randomized 1:1 to two treatment arms: Neflamapimod 40mg or placebo utilizing a central Interactive Web Response System (IWRS).

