### 6.2.2 Baseline and Change from Baseline

Baseline is defined as the last non-missing value (either scheduled, unscheduled or repeat) before the subject receives first dose of study drug (Day 1). Visit 3 (Day 1) date is defined as the date of the first dose.

Baseline score of MMSE for each subject is calculated using the average of Screen and Day 1 measurements.

Change from baseline  $CHG = AVAL - BASE$  where  $AVAL$  is the post-baseline value,  $BASE$  is the baseline value.

Baseline z-score will be used as a covariate in the MMRM and ANCOVA analysis. It will be calculated as below:

For baseline total recall, a z-score for each subject is defined by  $z = (x - m) / s$  where  $x$  is the subject's total recall at baseline, and  $m$  and  $s$  are the overall mean and overall standard deviation of total recall at baseline across all subjects. Similarly, a baseline z-score for each subject for delayed recall can be calculated.

A composite baseline z-score for each subject is calculated using equal weighting in the following way:

$Z = 0.5 * z\text{-score for total recall at baseline} + 0.5 * z\text{-score for delayed recall at baseline}$ .

The calculation method can be referenced to [Section 6.2.12](#).

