## 6.10 Efficacy Analyses

All efficacy analyses will be based on the Evaluable Efficacy Population by randomized treatment regardless of the treatment actually received. Descriptive statistics by treatment group

and visit will be reported for all efficacy endpoints. All statistical tests will be performed using a two-tailed 5% overall significance level, unless otherwise stated. All comparisons between treatments will be reported with 95% confidence intervals for the difference.

There will be no imputation of missing efficacy data.

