### 6.10.2 Primary Efficacy Analysis

The primary endpoint will be analyzed using Mixed Model for Repeated Measures (MMRM) with fixed effects for treatment, background AD-specific therapy (cholinesterase inhibitor or memantine versus no cholinesterase inhibitor or memantine), CDR-Global Score of 0.5 versus 1.0, scheduled visit (nominal) and scheduled visit by treatment interaction, random effect for subject and baseline z-score as a covariate. Least-square means (LSM) and 2-sided 95% confidence intervals (CI) will be provided for treatment group differences and estimated endpoint values by visit.

The normally-distributed assumption for the combined change in z-scores of total recall and delayed recall on the HVLT-R will be examined (at 0.05 alpha level). In case the assumption is violated, rank transformed data will be applied to the MMRM model. Ranks will be determined separately within each time point, based on observed data only.

In addition, Scale plot will be provided for combined change in z-scores of total recall and delayed recall on the HVLT-R at each post-baseline visit by treatment group.

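### The SAP does not settle the baseline covariate for the WMS and CDR-SB models; read literally it is the HVLT-R baseline z-score, at a modest cost in precision

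*SAP*

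**What the plan says.** - **Primary model.** SAP 6.10.2 specifies an MMRM with treatment, background AD therapy, CDR-Global (0.5 versus 1.0), visit and visit by treatment, plus "random effect for subject and baseline z-score as a covariate".
- **What the z-score is.** SAP 6.2.2 states: "Baseline z-score will be used as a covariate in the MMRM and ANCOVA analysis". Its definition begins "For baseline total recall, a z-score for each subject is defined by" and then averages the total recall and delayed recall z-scores. Both are HVLT-R scores. No z-score is defined for WMS or CDR-SB.
- **WMS and CDR-SB.** SAP 6.10.4 gives one sentence: "The same method used for the primary efficacy analysis will be applied for the analyses of the change in WMS", continuing to CDR-SB. It names no covariate.
- **MMSE and CSF biomarkers.** The next paragraph of 6.10.4 does name one, in an ANCOVA with treatment, background therapy and "CDR-Global Score as main effects and the baseline assessment as the covariate".
- **Protocol.** Section 8.5.1 leaves the specific efficacy analyses to the SAP, so it does not settle the matter.

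**The concern.** Own baseline is usually the strongest available predictor of change. If the model carries a different instrument's baseline, two things follow. The residual variance is larger than it need be, and a chance difference between arms in baseline WMS or CDR-SB passes in part into the estimated treatment difference.

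These endpoints have uses beyond this trial. Protocol 1.3 reports the Study 302 recall improvement on WMS, and it intends the CDR results to inform the size of effect for Phase 3 planning. The subgroup analyses of secondary endpoints in SAP 6.10.6 would inherit whichever covariate is used. Two different models satisfy the text, so the choice is left to the time of analysis.

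**Working it through.** **1. The plan's own figure.** SAP 4 states that up to 76 per arm "provides 90% power to detect ES of 0.53 and 80% power to detect ES of 0.46". SAP 5 gives 1:1 allocation, and SAP 6.10 a two-tailed 5% level. Power = Φ(ES × √(n/2) − 1.96), with √(76/2) = 6.164:
- ES 0.53: Φ(3.267 − 1.96) = 90.4% (noncentral t 90.1%).
- ES 0.46: Φ(2.836 − 1.96) = 80.9% (noncentral t 80.4%).

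The statement reproduces. This calculation contains no covariate term, so the point below does not touch it.

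**2. Set-up for the covariate question.** One post-baseline visit, own-baseline SD set to 1, and:
- k = follow-up SD divided by baseline SD;
- ρ = correlation of the endpoint's own baseline with its follow-up value;
- r = correlation of that baseline with the HVLT-R baseline z-score, which is taken to relate to follow-up only through own baseline.

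The documents give neither ρ nor r. Assumed ranges: ρ 0.6-0.8, r 0.3-0.7.

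Formulas:
- Slope of change on own baseline: ρk − 1.
- Residual variance given own baseline: k²(1 − ρ²).
- Residual variance given HVLT-R z: k² + 1 − 2ρk − r²(ρk − 1)².

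**3. Equal variances (k = 1).**
- ρ 0.6, r 0.3: (0.8 − 0.09 × 0.16)/0.64 = 0.7856/0.64 = 1.23.
- ρ 0.7, r 0.5: (0.6 − 0.25 × 0.09)/0.51 = 0.5775/0.51 = 1.13.
- ρ 0.8, r 0.7: (0.4 − 0.49 × 0.04)/0.36 = 0.3804/0.36 = 1.06.

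The increase is 6-23%, equivalent to losing about 5-19% of the sample (1 − 1/1.057 to 1 − 1/1.228). An effect with 80% power under own-baseline adjustment would have about 72-78%.

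**4. Study 302 spreads.** Protocol 1.3 gives ±3.8 then ±4.3 for WMS immediate recall (k = 1.13) and ±2.3 then ±4.1 for delayed recall (k = 1.78), baseline to Day 84. It does not say whether ± is an SD or a standard error. The ratio is the same either way if the same subjects contribute at both times.

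| Endpoint | Slope on own baseline | Lowest ratio | Highest ratio |
|---|---|---|---|
| WMS immediate | −0.32 to −0.09 | 0.4655/0.4610 = 1.01 (ρ 0.8, r 0.7) | 0.9133/0.8195 = 1.11 (ρ 0.6, r 0.3) |
| WMS delayed | +0.07 to +0.43 | 2.0362/2.0337 = 1.00 (ρ 0.6, r 0.7) | 1.3092/1.1440 = 1.14 (ρ 0.8, r 0.3) |

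For delayed recall at ρ 0.6-0.7 the increase is only 0-3%.

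**5. Chance imbalance.** A 0.2 SD own-baseline difference between arms shifts the estimate by 0.2 × (ρk − 1) × (1 − r²), in baseline SDs. With k = 1 and ρ = 0.7, the size is 0.2 × 0.3 × 0.51 = 0.03 (r 0.7) to 0.2 × 0.3 × 0.91 = 0.055 (r 0.3). Own-baseline adjustment removes this.

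**6. Simulation check (k = 1, 4,000 trials per setting, 76 per arm).** For (ρ, r) = (0.7, 0.5), (0.5, 0.5) and (0.8, 0.3), the variance ratios were 1.13, 1.25 and 1.12; the formula gives 1.13, 1.25 and 1.10. Mean estimates were about zero under both covariates, so there is no systematic bias. The slope of the estimate on own-baseline imbalance was −0.22, −0.37 and −0.19 with HVLT-R z, and about zero with own baseline.

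CDR-Global and the repeated visits were not modelled.

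**The case against.** The strongest reply is that the literal reading is not the natural one. In the primary model the baseline z-score is the analysed endpoint's own baseline, so the same method for WMS ordinarily means adjusting for baseline WMS. Some substitution is needed anyway: 6.10.2 ties its normality check to the HVLT-R combined change, and nobody would let that decide whether WMS is rank-transformed. Nor can the 6.2.2 sentence govern every model, because the MMSE and CSF ANCOVAs use their own baseline. This stands as a plausible reading. It does not close the matter, since 6.10.4 names own baseline where it means it and is silent for WMS and CDR-SB.

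A reader might infer more than the documents support:
- **That the wrong covariate has been chosen.** The text is open between two models.
- **That own-baseline imbalance is unadjusted.** The HVLT-R baseline captures some correlated WMS imbalance. CDR-Global, a stratification factor and model term, captures CDR-SB coarsely.
- **That the shell column in SAP 11 shows the HVLT-R model will be re-used.** That column is a layout reference. Several adverse-event tables cite shell 14.2.4.1, an HVLT-R table, while the WMS immediate and CDR-SB MMRM tables cite none.
- **That change must be negatively related to own baseline.** With the Study 302 delayed-recall spreads the slope is positive over the assumed range.

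Study 302 was small (n=15 at Day 84) and uncontrolled, but it is the only information on WMS spread in the documents.

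**Conclusion.** The point holds as an unresolved specification with a modest cost under one of its two readings. If the HVLT-R z-score is carried over, the treatment estimates for WMS and CDR-SB remain unbiased under randomisation, but they are somewhat less precise and only partly protected against chance own-baseline imbalance.

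The size rests on assumed correlations and on the variance ratio. The equal-variance range of 6-23% is an upper guide, and the Study 302 ratios bring it down to 1-11% for WMS immediate and 0-14% for WMS delayed. For CDR-SB the loss is probably below the equal-variance figure because CDR-Global is already in the model; by how much was not calculated.

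The consequence is limited. The primary analysis and its power statement do not change, and SAP 6.10.7 treats all secondary endpoints as descriptive. The correction is still worth making because it is free and removes a model choice from the analysis stage.

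**What to change.** - **SAP 6.10.4:** state that the MMRM for each WMS composite (immediate, delayed, combined) and for CDR-SB is the primary MMRM with the baseline z-score replaced by the baseline value of the endpoint analysed.
- **SAP 6.2.2:** limit the sentence on the z-score covariate to the HVLT-R composite analyses.
- **SAP 6.10.6:** no separate edit is needed if the subgroup models follow 6.10.4.

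No further model term is required. The cost is two sentences. WMS is collected on Day 1 and CDR at Screening (Protocol Table 6-1), and the general baseline definition in SAP 6.2.2 already covers both. If the sponsor always meant own baseline, the edit only records it.

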#### 6.10.5 Exploratory Analyses

Additional exploratory analyses may be performed to further study the effects of treatment as data warranted. Numerical exploratory endpoints will be analyzed using analysis of covariance, t-tests, or Wilcoxon sign rank test. Analysis of categorical exploratory endpoints will be performed using chi-square test. Exploratory endpoints include

- Change of total recall on the HVLt-R
- Change of delayed recall on the HVLt-R
- Change of retention (%) on the HVLt-R
- Change of recognition on the HVLt-R
- Change of recognition on the WMS
- Subgroups analyses by , sex (male/female), age (dichotomized at pretreatment median age), race (white vs. non-white, Hispanic vs. non-Hispanic), CYP2C19 genotype status and/or other grouping covariates, if data permit.
- Outlier analyses to identify the impact of any extreme values on the analysis results.
- Categorical exploratory endpoints (i.e. responder analysis), if data permit, will be performed using Pearson's chi-square test

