14.2.3.3	Mixed Models for Repeated Measures Analysis of Combined Change from Baseline in Z-score of Total Recall and Delayed Recall on the Hopkins Verbal Learning Test – Revised (HVLTR) Per-Protocol Population	Stat IP	14.2.1.3
14.2.3.4	Analysis of Covariance of Combined Change from Baseline in Z-score of Total Recall and Delayed Recall on the Hopkins Verbal Learning Test – Revised (HVLTR) Efficacy Population	Stat IP	
14.2.3.5	Analysis of Covariance of Combined Change from Baseline in Z-score of Total Recall and Delayed Recall on the Hopkins Verbal Learning Test – Revised (HVLTR) Per-Protocol Population	Stat IP	
14.2.4	Exploratory Endpoints		
14.2.4.1	Analysis of Covariance of Change from Baseline in Total Recall on the Hopkins Verbal Learning Test – Revised (HVLTR) Efficacy Population	IP	
14.2.4.2	Analysis of Covariance of Change from Baseline in Delayed Recall on the Hopkins Verbal Learning Test – Revised (HVLTR) Efficacy Population	IP	14.2.4.1
14.2.4.3	Analysis of Covariance of Change from Baseline in Retention (%) on the Hopkins Verbal Learning Test – Revised (HVLTR) Efficacy Population	IP	14.2.4.1
14.2.4.4	Analysis of Covariance of Change from Baseline in Recognition on the Hopkins Verbal Learning Test – Revised (HVLTR) Efficacy Population	IP	14.2.4.1
14.2.4.5	Analysis of Covariance of Change from Baseline in Wechsler Memory Scale (WMS) Recognition Composite Tests of Logical Memory II, Verbal Paired Associates II and Visual Reproduction II (0-60) Efficacy Population	IP	14.2.4.1

14.2.4.6.x	Subgroup Analysis of Covariance of Combined Change from Baseline in Z-score of Total Recall and Delayed Recall on the HVLTL-R Efficacy Population	IP	
14.2.4.7	Pearson's Chi-square Test for Responder Efficacy Population	IP	
14.2.5-14.2.6	Subgroup Analyses		
14.2.5.1.1	Hopkins Verbal Learning Test – Revised (HVLTL-R), Cholinesterase Inhibitor or Memantine Efficacy Population	IP	
14.2.5.1.2	Hopkins Verbal Learning Test – Revised (HVLTL-R), No Cholinesterase Inhibitor or Memantine Efficacy Population	IP	
14.2.5.2.1	Combined Change from Baseline in Z-score of Total Recall and Delayed Recall on the Hopkins Verbal Learning Test – Revised (HVLTL-R), Cholinesterase Inhibitor or Memantine Efficacy Population	IP	
14.2.5.2.2	Combined Change from Baseline in Z-score of Total Recall and Delayed Recall on the Hopkins Verbal Learning Test – Revised (HVLTL-R), No Cholinesterase Inhibitor or Memantine Efficacy Population	IP	

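### The exploratory responder analysis is an unadjusted chi-square on an undefined responder; adjusting for baseline would gain some power, by an amount that depends on a correlation the plan does not give

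*SAP*

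**What the plan says.** SAP 6.10.5 states: "Categorical exploratory endpoints (i.e. responder analysis), if data permit, will be performed using" Pearson's chi-square test. The table list in SAP 11 has one matching entry, Table 14.2.4.7: "Pearson's Chi-square Test for Responder Efficacy Population". No covariate, stratum or adjusted companion table is named. The documents also do not define a responder: there is no score, cut-off, visit or expected rate.

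Elsewhere the SAP adjusts:
- SAP 5: "Randomization was stratified by 1) background AD-specific therapy", and by CDR-Global 0.5 versus 1.0.
- SAP 6.10.2: the primary MMRM carries both factors, with "random effect for subject and baseline z-score as a covariate".
- SAP 6.10.3: the sensitivity ANCOVA uses both factors and the baseline z-score.
- SAP 6.10.4: WMS and CDR-SB follow the primary method. MMSE and CSF biomarkers use ANCOVA with both factors and their own baseline.

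The standing of the analysis is clear. SAP 6.10.5 opens: "Additional exploratory analyses may be performed to further study the effects of treatment as data warranted".

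**The concern.** All the numerical endpoints above are changes from baseline. If the responder is a threshold on such a change, regression to the mean makes response more likely for subjects who start low. An unadjusted test leaves that explainable variation in the error, although the baseline z-score is already derived in SAP 6.2.2 and both factors are already in the primary model.

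What is at stake is efficiency and consistency. The responder table will be read beside an adjusted MMRM, and it would be less sensitive than the same data allow.

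**Working it through.** **Inputs from the documents.** Size (SAP 4): "Up to 76 subjects per treatment arm (152 total"). Power of 80% at effect size 0.46 and 90% at 0.53 (SAP 4). Two-sided 5% (SAP 6.10). 1:1 allocation (SAP 5).

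**Not in the documents, so assumed.** The responder cut-off, and the baseline/Week 24 correlation rho (range 0.3 to 0.9).

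**1. The plan's own figure.** Power ≈ Φ(ES × √(76/2) − 1.96).
- ES 0.46: 0.46 × 6.164 = 2.836, and Φ(0.876) = 80.9% (80.4% with the t distribution).
- ES 0.53: 0.53 × 6.164 = 3.267, and Φ(1.307) = 90.4% (90.1% with t).

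The stated power reproduces. It is for a difference in means; no power is stated for responders.

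**2. Effect of dichotomising.** Scale change to SD 1 and cut midway between the arm means. At ES 0.46 the response rates are Φ(±0.23) = 59.1% and 40.9%, a difference of 0.182. The null standard error is √(2 × 0.25/76) = 0.0811 and the alternative one is √(2 × 0.591 × 0.409/76) = 0.0798. Power ≈ Φ((0.182 − 1.96 × 0.0811)/0.0798) = Φ(0.29) ≈ 61%. Simulation gives about 59% to 61%. About 20 points go through dichotomising, before any question of adjustment.

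**3. Effect of baseline adjustment.** With equal variances at both visits, corr(change, baseline) = −√((1 − rho)/2), so baseline explains R² = (1 − rho)/2 of the change. Simulated power at ES 0.46, 76 per arm, midway cut, 8000 trials per setting, for Pearson and for logistic regression with a likelihood-ratio test:

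| rho | R² | Pearson | Adjusted | Gain (points) |
|---|---|---|---|---|
| 0.3 | 0.35 | 59.4% | 72.9% | 13.5 |
| 0.5 | 0.25 | 60.4% | 69.3% | 8.9 |
| 0.7 | 0.15 | 60.5% | 67.3% | 6.8 |
| 0.8 | 0.10 | 59.7% | 64.8% | 5.1 |
| 0.9 | 0.05 | 59.0% | 62.7% | 3.7 |

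The first three rows include two non-prognostic strata in the model. Monte Carlo error of each power is about √(0.6 × 0.4/8000) = 0.5 points. A separate run of 3000 trials per setting gave gains of about 13, 9, 6, 5 and 3. At ES 0.53 the gains are 12.1, 8.9 and 6.0 points for rho 0.3, 0.5 and 0.7 (71.9% to 84.0%, 72.0% to 80.9%, 71.5% to 77.5%).

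**4. Sensitivity to the cut-off.** With the cut placed so that 30% or 50% of controls respond, at either effect size, the gains (Wald to likelihood-ratio test) are:
- R² 0.36 (rho 0.28): 9.6 to 11.1 points.
- R² 0.25 (rho 0.5): 5.1 to 7.5 points.
- R² 0.16 (rho 0.68): 3.1 to 4.5 points.
- R² 0.10 (rho 0.8; 50% control rate only): 1.8 to 2.7 points.
- R² 0.04 (rho 0.92): 0.2 to 1.4 points.

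These are mostly 2 to 3 points below the table, largely because Pearson is slightly conservative when overall response is close to one half, as under the midway cut.

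**5. Share due to test size.** Null rejection at the midway cut was 4.2% to 4.7% for Pearson and 4.9% to 5.5% for the adjusted test. At 60% power the noncentrality is 1.960 + 0.253 = 2.213. Raising the size from 5.0% to 5.5% moves the critical value to 1.919, and Φ(0.294) = 61.6%, a gain of 1.6 points. Counting Pearson's conservatism as well, 4.4% against 5.3% gives Φ(0.199) = 57.9% against Φ(0.278) = 60.9%, or 3 points.

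**6. Strata alone.** A Cochran-Mantel-Haenszel (CMH) test over the four strata changes power by −1 to 0 points when the strata explain up to 5% of the underlying score, 0 to +1 at 10%, and about +2 at 20%.

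**The case against.** The strongest case is that the choice is legitimate. The analysis is exploratory, optional and unpowered. The primary and secondary inferences already adjust. SAP 6 allows further tests in the study report, and SAP 6.10.5 permits unadjusted t-tests for numerical exploratory endpoints too, although the table list shows ANCOVA for those. All of this stands, and it limits the importance of the point.

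The size is also open to challenge. Protocol 3.2 describes the HVLT-R as highly reliable on retest, which points to a higher rho and a smaller gain. That stands as a reason not to favour the low end of the range, but the protocol gives no value at Week 24, so it does not fix rho.

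A reader might infer three stronger things that the documents do not support:
- **A fixed loss of power.** No definite figure can be derived, because the cut-off and rho are both unstated.
- **Lost power from ignoring the stratification.** The strata recover almost nothing unless they are strongly prognostic.
- **That a responder result at odds with the MMRM would reflect only the missing adjustment.** Dichotomising costs about 20 points by itself, more than the adjustment restores, so the two could still disagree after the change.

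**Conclusion.** The point holds as a minor, inexpensive improvement. The responder test is unadjusted, against the SAP's own practice for its main models. If response is a cut on change from baseline, midway between the arm means, baseline adjustment at 76 per arm gains about 6 to 13 points for rho from 0.7 down to 0.3. For rho of 0.8 to 0.9 it gains about 2 to 5 points, and nearer 1 at the top of that range with the other cut-offs tried. About 1.5 to 2 of these points are test size rather than information.

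If response is not defined on change, the gain depends on how well baseline predicts the score and could be nil. The current test remains valid: leaving out the covariates costs efficiency and does not inflate type I error. The primary conclusion is not affected. The more basic gap is that no responder is defined, and without a definition neither test can be run as pre-specified.

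**What to change.** In SAP 6.10.5 and Table 14.2.4.7:
1. Pre-specify the responder: which score, which cut-off, which visit.
2. Replace Pearson's chi-square with a logistic regression on treatment, background AD therapy (yes/no), CDR-Global (0.5/1.0) and the baseline of the same score (the baseline z-score if the responder is built on the HVLT-R composite).
3. Report a standardised risk difference with 95% CI. This keeps a comparison of arm-level response rates, whereas the model's odds ratio is conditional on the covariates.
4. Keep Pearson, or CMH over the randomisation strata, as the fallback if responders are sparse, noting that it recovers little power.

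The cost is a short SAP edit including the definition, somewhat more programming, and a less simple table. The randomisation factors and the baseline scores are already collected, so no new data are needed.
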